A randomized control study will be conducted and include 90 child care centers in four CA counties enrolled in five 9-month cycles over five years. The counties will be matched on rates of poverty, number of children under age five, and annual pesticide usage. The matched counties will be randomly assigned to an IPM intervention or an active control intervention (i.e. physical activity). During the 7-month Intervention phase, trained child care health consultants will host one workshop per center on the intervention topic (IPM or physical activity) and conduct seven monthly consultations per center starting with the center director and the child care health consultant setting center-specific goals.

The 'Follow-Up Study' will assess IPM practices, pests, and pesticides in all of the enrolled child care centers. The directors will complete surveys, the research staff will conduct observations, and a researcher will collect dust samples in the child care centers the same season and month as the baseline period.

BACKGROUND AND SIGNIFICANCE: Briefly provide the background and significance of this study (e.g. why is this study needed) (space limit: one page):

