13. Health and Safety Checklist for Early Care and Education Programs ([name] et al., 2015)
14. Pesticide Use Data - collected by the CA Department of Pesticide Regulation

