Cover page

Official Project Title: Reducing Pesticide Exposures in Child Care Centers

NCT # 03319927

Document: **Statistical Analysis**

Plan Document Date 8/13/2025

Statistical Analysis Plan

Frequency tables for all the variables and measures of central tendency and variability for continuous variables were stratified by randomization group to check for imbalances. If the two groups differ significantly at baseline on covariates, we will use methods based on the Rubin causal model (e.g., propensity scores, double-robust estimation) to obtain the desired population-level estimates under the counterfactual assumption of balanced groups. (Luellen, Shadish, & Clark, 2005; Rubin, 2004; Seaman & Copas, 2009; Shadish, Luellen, & Clark, 2006; Weitzen, Lapane, Toledano, Hume, & Mor, 2004) Descriptive analyses will also yield important information about the child care centers' levels of pesticide contamination and child exposures; these data were summarized by group, time, and cohort. Primary inferential analyses were performed using tobit regression models which provided an approach for modeling repeatedly measured and clustered dependent variables in this study. (Verbeke & Molenberghs, 2000) SAS (SAS Institute, 2002). Survey and observational data were analyzed using parametric or non-parametric statistics based on the distribution of the dependent variable aggregated by child care center (n=85). All tests used a priori $p < .05$ as level of statistical significance.

Specific Aim 1. To determine if a nurse-led IPM workshop improves child care center staff's IPM knowledge (a) **Unit of Analysis:** Child care staff aggregated by center. (b) **Dependent Variable:** IPM knowledge score. (d) **Independent Variables: Group and Time.** Paired ttests were conducted to assess change in knowledge at baseline and post-IPM workshop.

Specific Aim 2. To determine if an IPM intervention in child care centers (a) increases the number of IPM policies, (b) increases IPM practices, (c) decreases pest problems (i.e., number of pests present, pest debris), and (d) increases center director's self-efficacy. (a) **Unit of Analysis:** Child care centers. (b) **Dependent Variable:** IPM policy, IPM practices, pest problems, director self-efficacy. (c) **Independent Variables: Group and Time.** Normally distributed dependent variables were analyzed using ttests or ANOVA and non-normally distributed dependent variables were analyzed using Kruskal-Wallis tests.

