Specific Aim 3: To determine if an IPM intervention reduces pesticide contamination in the intervention IPM child care centers compared to the PA control centers. (a) **Unit of Analysis:** Child care centers. (b) **Dependent Variable:** Pesticide concentrations in dust. (c) **Independent Variables: Group, Time, and Cohort.** Tobit regression models were conducted with an additional random intercept term for child care center to account for correlations within centers across timepoints (baseline, post-intervention). The concentrations and detection of the 15 pesticides measured in dust were analyzed separately using the STATA command 'tobit'.

Specific Aim 4: To determine if an IPM intervention reduces children's exposure to pesticides in the IPM intervention child care centers compared to the children in the PA control centers. (a) **Unit of Analysis:** Enrolled children with complete wristband data at baseline and post-intervention aggregated by child care center. (b) **Dependent Variable:** Pesticides measured in children's wristbands worn at the child care. (c) **Independent Variables: Group, Time, and Cohort.** Pesticide concentrations analyzed in the silicone wristbands. (c) **Independent Variables: Group, Time, and Cohort.** Tobit regression models were conducted with an

additional random intercept term for child care center to account for correlations within centers across timepoints (baseline, post-intervention). The concentrations and detection of the 13 pesticides measured in dust were analyzed separately.

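### Counties are randomised, but the between-arm tests for Aims 2 to 4 treat centers as independent, so the nominal 5% level holds only if county-level correlation is zero

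*Protocol*

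**What the plan says.** Protocol Section 8.4 plans for "90 child care centers in four CA counties enrolled in five 9-month cycles over five years". It describes matching before allocation: "The counties will be matched on rates of poverty, number of children under age five, and annual pesticide usage". It then gives the unit of allocation: "The matched counties will be randomly assigned to an IPM intervention or an active control intervention (i.e. physical activity". Two counties per arm is the natural reading of four matched counties and two arms, but it is not written. Neither document describes randomisation of centers within counties.

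The SAP works at the level of the center:

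- **General methods.** Survey and observational data are analysed with the "dependent variable aggregated by child care center (n=85"). The significance rule is "All tests used a priori $p < .05$ as level of statistical significance".
- **Aim 1.** Paired t-tests of staff knowledge before and after the workshop, aggregated by center.
- **Aim 2.** t-tests or ANOVA, or Kruskal-Wallis tests, with centers as the units.
- **Aims 3 and 4.** Tobit models with group, time and cohort, plus an "additional random intercept term for child care center to account for correlations within centers across timepoints (baseline, post-intervention").

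No model contains county or matched pair. The SAP mentions no county-level degrees of freedom, randomisation test or ICC.

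**The concern.** In a cluster-randomised comparison, the error variance has to include variation between the randomised units. Here those units are counties. Centers in one county share local conditions, and pesticide exposure is an outcome for which that matters: the protocol itself matches counties on pesticide usage, and its parent questionnaire asks about residence near agricultural fields. If centers in a county move together between baseline and post-intervention, a center-level standard error leaves that component out. A change specific to one or two counties can then be read as an intervention effect.

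The center intercept does not help. By its own description it handles correlation within a center over time, not correlation between centers in the same county. The SAP's fallback of propensity or double-robust methods addresses measured covariate imbalance. It supplies neither county-level variance nor county-level degrees of freedom.

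At stake is whether a center-level result with p < .05 can be presented as confirmatory evidence from a randomised trial.

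**Working it through.** **Inputs from the documents.** Four counties, 90 centers planned and five cycles (Protocol 8.4). 85 centers analysed, stated for survey and observational data only, and alpha 0.05 with sidedness not given (SAP, general methods).

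**Assumptions.** Two-sided tests, two counties per arm, and a county ICC varied over a range because none is given. For a group-by-time contrast the ICC is that of the change from baseline, since stable county differences cancel there. For a comparison of post-intervention levels it is the ICC of the level.

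The plan gives no power calculation to reproduce, so the only stated figure that can be checked is the 5% level.

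**Formulas.** With m centers per cluster, the design effect is DE = 1 + (m − 1) × ICC. The actual type I error of a nominal 5% center-level test is 2 × [1 − Φ(1.96/√DE)].

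**Cluster size.** Two cases bracket the problem:

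- The county-specific change is the same in every cycle: m = 85/4 = 21.25.
- It is specific to each county and cycle, and every county enrols in every cycle (not stated): m = 85/(4 × 5) = 4.25.

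| Assumed ICC | DE, m = 21.25 | Effective centers (85/DE) | Type I error | DE, m = 4.25 | Type I error |
|---|---|---|---|---|---|
| 0 | 1.00 | 85 | 5.0% | 1.00 | 5.0% |
| 0.01 | 1.20 | 70.7 | 7.4% | 1.03 | 5.4% |
| 0.02 | 1.41 | 60.5 | 9.8% | 1.07 | 5.8% |
| 0.05 | 2.01 | 42.2 | 16.7% | 1.16 | 6.9% |
| 0.10 | 3.03 | 28.1 | 26.0% | 1.33 | 8.9% |

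Worked line: at ICC 0.05 and m = 21.25, DE = 1 + 20.25 × 0.05 = 2.01, so 1.96/√2.01 = 1.38 and the two-sided tail is 16.7%.

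**Simulation check (m = 21.25 case).** 40,000 null trials with counties of 22, 21, 21 and 21 centers, two counties per arm, and a two-sample t-test on centers gave 5.1%, 7.5%, 9.7%, 17.3% and 26.9% for the five ICC values. A t-test on the four county means held 4.9% to 5.1% throughout. The simulation used t-tests, not tobit models, so for Aims 3 and 4 the table is only a guide.

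**What four counties can support, whatever the ICC.**

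- Free two-against-two allocation: C(4,2) = 6 allocations, so the smallest two-sided randomisation p-value is 2/6 = 0.33.
- Two matched pairs: 2² = 4 allocations, so the smallest is 2/4 = 0.50.
- t-test on county means: 2 df, critical value 4.30; matched-pair version: 1 df, critical value 12.7. The center-level test with 83 df uses 1.99.
- County-level model: 4 counties less intercept, pair and arm leaves 1 df. A county-level covariate leaves 0.

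**The case against.** The strongest reply is that the inflation is assumed rather than shown. The documents give no ICC, and at zero the 5% level is correct. Stable county differences cancel in a group-by-time contrast. Enrolment is spread over five cycles and cohort is a term in Aims 3 and 4, so county shocks may well be cycle-specific, which puts the error rate in the right-hand column of the table. All of this stands, and it is why both cases are shown. It does not explain why the ICC should be taken as zero without saying so.

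Three stronger readings are tempting, and the documents do not support them:

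- *A reader might infer that every planned test is affected in the same way.* The Aim 1 paired t-test is a pre/post test, not a comparison of randomised arms, so the randomisation argument does not apply to it. It does still assume independent centers; a within-arm test of change simulated at 7.3% for an ICC of 0.01. Nor can 85 be carried over to Aims 3 and 4, for which no number of centers is stated.
- *A reader might infer that arm and county are fully confounded.* With two counties per arm, county is nested in arm with some replication, and the counties were matched on three factors, including pesticide usage. Two pairs cannot guarantee balance, but this is not one county per arm. Climate and local consultants as county differences are not in the text.
- *A reader might infer that a county random effect would cure the problem.* With 1 df or none it would not. Adding "Pesticide Use Data - collected by the CA Department of Pesticide Regulation" (Protocol 8.11, item 14) as a county covariate would use the last degree of freedom, and the entry states neither its geographic level nor that the study holds the data.

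**Conclusion.** The unit of randomisation and the unit of inference disagree for the between-arm tests in Aims 2 to 4, and nothing in either document repairs this. The nominal 5% level rests on an unstated assumption of zero county-level ICC. For an assumed ICC of 0.01 to 0.10 and 85 centers, the actual level is about 7.4% to 26% if county changes persist across cycles, and about 5.4% to 8.9% if they are cycle-specific and every county enrols in each cycle. The size within that range is unknown. It would be too strong to say that the p-values are certainly too small, or by how much.

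The limit on randomisation-based inference does not depend on the ICC: with two counties per arm, no test based on the allocation can reach 0.05. This is a limitation of the design that analysis cannot remove. The SAP can only disclose it and show its effect.

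**What to change.** First confirm which unit was randomised.

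If counties were randomised:

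1. Report the group-by-time difference-in-differences for Aims 2 to 4 separately for each matched county pair, so that the reader can see whether the two pairs agree.
2. Add a sensitivity table giving the Aim 2 to 4 standard errors and p-values over a stated range of county ICC, for both cluster definitions above, using the number of centers actually in each analysis.
3. State in the SAP that center-level p-values are conditional on these four counties, lack randomisation-based protection, and do not support confirmatory claims at p < .05 of an intervention effect.

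Do not rely instead on a county random effect with pair and county covariates, because four counties leave 1 or 0 degrees of freedom.

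If centers were in fact randomised within counties, correct Section 8.4 and add county as a fixed stratification factor in the Aim 2 to 4 models.

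The cost is some re-analysis and a less favourable statement of the evidence. No new data are needed.

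### The counties are matched before randomisation but no SAP model uses the matching, so with unequal center counts a pair-specific change over time biases the arm-by-time estimate

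*Protocol*

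**What the plan says.** Protocol 8.4 (Design) plans to "include 90 child care centers in four CA counties enrolled in five 9-month cycles over five years". It then states: "The counties will be matched on rates of poverty, number of children under age five, and annual pesticide usage". The next sentence gives the unit of randomisation: "The matched counties will be randomly assigned to an IPM intervention or an active control intervention (i.e. physical activity". The word pair is not used. Two pairs, each with one county per arm, is inferred from four matched counties and two arms.

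The SAP does not carry the matching forward:

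- **Aims 3 and 4** (dust and wristband pesticides): Tobit models with "Independent Variables: Group, Time, and Cohort" and a random intercept for center.
- **Aim 2** (policies, practices, pests, director self-efficacy): "Independent Variables: Group and Time", by t-test, ANOVA or Kruskal-Wallis.
- **Aim 1**: paired t-tests that "were conducted to assess change in knowledge at baseline and post-IPM workshop". This is a within-center comparison, so the point below does not concern it.

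The only other adjustment is in the SAP's opening paragraph. Propensity or double-robust methods are used if the arms differ significantly on baseline covariates. That step names neither pair, county nor the matching factors. The same paragraph gives the number of centers analysed, in the phrase "distribution of the dependent variable aggregated by child care center (n=85", with no split by county.

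**The concern.** The matching factors were presumably chosen because they bear on the outcome. Annual pesticide usage is the plainest case, since pesticides in dust and on wristbands are the outcomes of Aims 3 and 4. If the analysis ignores the pairs, comparability rests on each pair supplying the same share of centers to both arms.

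A pair difference in level is not the problem, because a before-to-after contrast within center removes it. A pair difference in change is not removed. Protocol 8.6 says that it is unknown whether season affected the year 1 dust comparison, and that no post-intervention dust was collected in the baseline season and month. The follow-up study returns to the baseline season, but the Aim 3 model in the SAP uses only baseline and post-intervention. If seasonal change differs between a high-usage and a low-usage pair, and the pairs are unevenly represented in the arms, part of that difference would be read as an intervention effect or would mask one.

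**Working it through.** The plan states no power, effect size, SD or intraclass correlation (ICC), so there is no planned figure to reproduce.

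**Inputs from the documents.** 4 counties, 2 arms, 85 centers analysed, significance level 0.05 (taken as two-sided).

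**Assumptions.** Two pairs, A and B. A linear change score stands in for the arm-by-time contrast, and Tobit censoring is not modelled. SD of change within county is 1. Pair A changes by d more than pair B, with d = 0.5 or 1. The arms have 43 and 42 centers. There is no true arm effect.

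**Step 1, bias without a pair term.** Bias = d x (share of IPM centers in pair A minus share of control centers in pair A). Rejection rates are simulated with no county variation beyond the pair difference.

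| Centers, IPM/control: pair A; pair B | Share difference | Bias, d = 0.5 | Bias, d = 1 | Null rejection, d = 0.5; d = 1 |
|---|---|---|---|---|
| 21/21; 22/21 | 21/43 - 21/42 = -0.012 | -0.006 | -0.012 | 4.4%; 2.7% |
| 25/20; 18/22 | 25/43 - 20/42 = 0.105 | 0.053 | 0.105 | about 5%; about 5% |
| 28/16; 15/26 | 28/43 - 16/42 = 0.270 | 0.135 | 0.270 | about 9%; about 17 to 18% |

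For scale, the SE of the arm difference is sqrt(1/43 + 1/42) = 0.217.

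**Step 2, near-equal counts.** The pair difference stays in the residual. The model SE is multiplied by sqrt(1 + d^2/4): sqrt(1.0625) = 1.03 at d = 0.5 and sqrt(1.25) = 1.12 at d = 1. This presumes that counties within a pair do not otherwise differ.

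**Step 3, effect of the pair term on the estimate.** The bias becomes zero for every split. For 28/16 and 15/26 the SE is 1/sqrt(28 x 16/44 + 15 x 26/41) = 1/sqrt(10.18 + 9.51) = 0.225. At d = 0.5 the root mean squared error without the pair term is sqrt(0.135^2 + 0.217^2) = 0.256, so it falls from about 0.26 to about 0.23.

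**Step 4, effect of the pair term on the error rate.** With no further county variation, the null rejection rate with the pair term is about 5% for every split. With a county ICC of change of 0.05 it is not:

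- Near-equal counts: from 15.5% without the pair term to 16.9% with it at d = 0.5, and from 12.8% to 17.4% at d = 1.
- A roughly 2:1 split (28/14; 15/28), d = 0.5: from 22.4% to 16.5%.

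So the pair term helps the error rate when counts are very uneven and slightly hurts it when they are near equal. In both cases it leaves the rate at about 16 to 17%.

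**The case against.** The strongest reply is that the bias depends on two quantities that the documents do not give, and that the larger defect lies elsewhere. With near-equal counts there is almost nothing to correct. The bias belongs to one realised allocation and averages out over re-randomisation. Seasonal change that differs by pair is a conjecture, since the protocol says only that seasonal effects are unknown. Matched counties could also mean one matched set of four, which leaves no pair to model. All of this stands as a limit on the size and certainty of the point. It does not answer the point that the plan matches on a factor tied to the outcome and never uses it. The sponsor can settle both the counts and the matching structure from data already held.

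Three stronger readings are tempting and are not supported:

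- A reader might infer that imbalance is certain because neither 90 nor 85 divides by four. Equal shares do not need that: 90 = 23/23 + 22/22, and 85 = 24/16 + 27/18, where 24/51 = 16/34.
- A reader might infer that any imbalance inflates false positives. At 25/20 and 18/22 the rate stays near 5%, and only the estimate shifts.
- A reader might infer that the present error bars are too wide, or that a pair term restores a 5% error rate. Both hold only if counties within a pair do not otherwise differ, which nothing in the documents supports.

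A degrees-of-freedom objection also has some force. An analysis of the two pair differences has 1 degree of freedom and a critical t of 12.7. That is a cost of county-level inference. It is not a reason to leave the pair out of the center-level point estimate.

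**Conclusion.** The point holds in a limited form. The matching is in the design and in no SAP model. If center counts differ across counties and the pairs change differently over time, the arm-by-time estimate is biased by 0.105 to 0.27 times the pair difference for the two uneven splits shown. That is 0.05 to 0.27 SD of change for pair differences of 0.5 to 1 SD. With near-equal counts the bias is negligible. The only effect is then a model SE about 3% larger at a 0.5 SD pair difference, provided counties within a pair do not otherwise differ.

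The result rests on two inferred pairs, an assumed pair difference, illustrative counts, a linear stand-in for the Tobit model, and the arm effect being read as a difference in change. The pair term repairs the estimate and not the inference, because the county is the randomised unit. It is worth making as a cheap improvement, alongside a treatment of county-level variation and not in its place.

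**What to change.** 1. State the matching structure, and report center counts by county and arm for each aim's analysis set. If there was one matched set of four and no pairs, say so; a pair term would then not apply.
2. Aims 3 and 4: add Pair and Pair x Time to the Tobit models. Pair alone is not enough, because a pair main effect cancels from a within-center change.
3. Aim 2: use ANOVA or regression on center-level change with a Pair term. For non-normal outcomes use a pair-stratified rank test, since t-tests and Kruskal-Wallis cannot take a Pair term.
4. State that the pair term does not make the standard errors valid, and pair it with an analysis that treats the county as the randomised unit. With two pairs, that analysis has 1 degree of freedom.
5. The SAP reports its analyses in the past tense, so label the new terms post hoc if results have been seen.

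The cost is one or two center-level degrees of freedom, replacement of the simple Aim 2 tests, and a rerun of the models. No new data are needed.

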Overview. The study participants include 90 child care center directors, 270 child care center staff, and 450 parents (mothers, fathers or legal guardians) and their preschool-age children, 3-5 years of age. The participants will be involved in the following procedures: (a) child care center directors will be interviewed by the UCSF research staff, (b) child care center staff will attend an educational workshop and complete a knowledge survey before and after the workshop, (c) parents/guardians will be given surveys to complete on their own or by interview about their family and child demographics and pesticide use at home, (d) children will have their height, weight, and waist circumference measured twice along with measurement of individual exposures using silicone wristbands before and after the intervention, and (e) research staff will collect dust samples in each center and conduct observations of the child care center environment and children's physical activity before and after the intervention.

Staff Roles. The research assistants' (RA) and child care health consultants' (CCHC) activities include:

1. Attend a one-day training on the intervention and data collection protocols. (CCHC/RA). The RA will achieve 90% inter-rater reliability with the PI on 2 observation instruments (Health and Safety Checklist and IPM Checklist).
2. Recruit child care directors through the local Resource and Referral Agencies (CCHC/RA).
3. Obtain signed consent forms from the child care directors (CCHC).
4. Identify 5 children per center and contact families and obtain signed consent forms. (CCHC/RA)
5. Conduct child care director interviews pre- and post-intervention (CCHC).
6. Complete Health and Safety and IPM Checklists. (RA)
7. Write-up the summary of the Checklist with photographs and narrative. (RA)
8. Collect anthropometric measures of the children, including height, weight, and waist circumference on 5 children per center pre- and post-intervention. (CCHC/RA)
9. Collect dust samples in the center and wristband measures for 5 children per center over two days pre- and post-intervention. (RA and CCHC together)

10. Prepare and provide 2 workshops for child care staff. (CCHC)
11. Review Checklist summaries with the director and establish 3-5 goals of the intervention. (CCHC)
12. Assist the child care directors to develop written health and safety policies. (CCHC)
13. Conduct monthly on-site (x3) or off-site (x3) (email, mail, phone) consultation. (CCHC)

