14. Complete post-intervention measures (interview, dust and silicone wristbands, activity observations, anthropometric measures). (CCHC/RA)
15. Complete post-intervention observational Checklists (IPM Checklist, Health and Safety Checklist) and write up summary report comparing pre- and post-intervention findings. (RA)

Baseline Assessment. During the Baseline Assessment stage at each center, an experienced research assistant (not a CCHC) will complete *inspection checklists* in each center. The IPM Checklist,([name] et al., 2012) Health and Safety Checklist for Early Care and Education Programs,([name], 2015) and Policies Checklist, utilized in prior studies, will be completed in all centers. The *IPM Checklist* includes 73 items with 8 subscales (outdoor: garbage, exterior, play area; indoor: kitchen, bathrooms, play areas, storage, staff area) and for each subscale the pest problems are observed in that location by type and number or pest debris. Cronbach's alpha coefficients for the subscales showed a range of moderate reliability ($r=.38$ to $.61$)([name] et al., 2016a). For this project, the IPM Checklist will include additional items to identify the pesticides stored and used on-site by child care or facility staff, including active ingredients and U.S. EPA pesticide registration numbers. The *Health and Safety Checklist* includes 66 items in three relevant subscales on sanitation (e.g., handwashing, air quality), supervision (e.g., child-staff ratios), and equipment and furnishings (e.g., physical activity indoors and outdoors). The Health and Safety *Policy Checklist* assesses written policies for each child care center based on the national health and safety standards.([name] et al., 2009) The relevant policies for this study include IPM and physical activity.

During this period, the nurse CCHC assigned to the child care center will *interview the child care center's director* to collect information on personal (e.g., education level, years of experience) and center (e.g., staff turnover, facility age) demographics; the center's pest problems, pesticide use practices, and IPM policies and practices; the center's physical activity programs for children; the center's food service responsibilities, menus, and feeding practices; and the center's cleaning products, cleaning routines, and maintenance practices. The CCHC will also ask the director to complete a *self-efficacy survey* based on Bandura's SCT.(Bandura, 1977)

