Post-Intervention Phase. During this phase, a research assistant will re-assess the center using the same observational checklists described for the Baseline Assessment, and the CCHC will also repeat all other aspects of Baseline Assessment data collection, including a director interview, the self-efficacy survey, dust collection, silicone wristband collection (children and teachers) and its attendant data collection from families, and anthropometric measurements. At Post-Intervention, however, no new children will be enrolled to participate. The same families who participated at Baseline will be invited to participate again, provided their child still attends the center and intends to be present on the sampling days.

Follow-up Study. We will also conduct a one-year follow-up study on pesticide exposure for all of the intervention centers, including both dust analyses and assessment of pests and pesticide products .

Sampling Procedures. The silicone wristbands will be sent de-identified to [name] laboratory at Oregon State University and the child care center's dust samples will be sent to Southwest Research Institute (SwRI) located in San Antonio, TX for analysis of multiple pesticides. They will be analyzed within a year of data collection and we will store the amount of

wristband or dust that is left over for 5 years to use in possible future analyses of other environmental chemicals or health markers.

8.11 INSTRUMENTS: List all questionnaires, surveys, interview, or focus group guides that will be used for this study:

If the instruments are not complete or not available because they will be developed as part of this study, describe the basic content or include an outline and submit the final versions to the IRB with a modification for approval prior to use.

1. IPM and Physical Activity (PA) Knowledge Survey – pre and post-workshop
2. IPM and PA Policy Checklist
3. Director interview
4. IPM Checklist ([name] et al., 2012)
5. Director IPM Interview
6. Director and child care provider Self-Efficacy ([name] et al., 2003) – modified Bandura
7. Demographic Survey for child care providers - sex, age, ethnicity,
8. Demographic Survey for parents - sex, age, ethnicity, BMI, health
9. CHAMACOS parent interview -modified as self-completed survey with major life events, physical activity
10. Child Anthropometrics
11. Dust samples ([name] et al., 2012)
12. Child activity measure modified OSRAP (A [name] et al., 2014)

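### The consultant who coaches the director also collects the director's post-intervention reports, so self-efficacy (Aim 2d) and any interview-sourced Aim 2 outcome are open to differential reporting

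*Protocol*

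**What the plan says.** **Delivery.** Protocol 8.4 states that "trained child care health consultants will host one workshop per center on the intervention topic (IPM or physical activity" and that the consultants then give monthly consultations, beginning with goal-setting with the director. In Protocol 8.9, Staff Roles item 11 is "Review Checklist summaries with the director and establish 3-5 goals of the intervention. (CCHC" and item 12 is "Assist the child care directors to develop written health and safety policies. (CCHC".

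**Assessment.** Item 5 is "Conduct child care director interviews pre- and post-intervention (CCHC". The Baseline Assessment text places the interview with the center's own consultant ("During this period, the nurse CCHC assigned to the child care center will"). It covers pests, pesticide use and the center's IPM policies and practices. The self-efficacy instrument reaches the director the same way: "The CCHC will also ask the director to complete a" self-efficacy survey. Under Post-Intervention Phase, "the CCHC will also repeat all other aspects of Baseline Assessment data collection, including a director interview, the self-efficacy survey".

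**Looser wording.** Item 14 assigns the post-intervention measures, including the interview, to consultant and research assistant together. The Overview says "child care center directors will be interviewed by the UCSF research staff".

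**What is kept separate.** The inspection checklists are reserved at baseline for a research assistant who is not a consultant, and a research assistant repeats the observational checklists after the intervention.

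**Analysis.** SAP Specific Aim 2 lists policy, practices, pest problems and director self-efficacy as outcomes. It names no source instrument for any of them.

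**The concern.** After seven months of coaching, a director in an IPM center is asked about pests, pesticide use and confidence in pest management by the person who set the IPM goals. That gives a reason to report success. A director in a physical activity center is also interviewed by a familiar consultant, but one who coached a different topic, so the pull towards favourable IPM answers should be weaker. The active control equalises contact time; it does not equalise this pressure.

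Because the coaching falls between the two waves, measuring change from baseline would not subtract the shift. It would act in the direction of Hypothesis 2. The t-tests, ANOVA and Kruskal-Wallis tests planned for Aim 2 cannot separate a change in reporting from a change in the center.

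**Working it through.** The documents give no effect size, SD or power calculation for Aim 2, so there is no stated figure to reproduce. The point rests first on setting outcomes beside their possible sources.

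| Aim 2 outcome | Collected by the consultant | Collected by the research assistant |
|---|---|---|
| (a) Policies | Director interview | Policy checklist, grouped with the research assistant's checklists under Baseline Assessment, but not named in Staff Roles items 6 and 15 |
| (b) Practices | Director interview | IPM Checklist |
| (c) Pest problems | Director interview | IPM Checklist (pests by type and number, debris) |
| (d) Self-efficacy | Survey given out by the consultant | None |

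Exposure is therefore certain for (d). For (a) to (c) it depends on which source the analysis uses, which the SAP does not say.

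**Illustration of size.**

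Inputs: 85 centers (SAP opening section); significance level 0.05 (same section). Assumptions: two-sided test, arms of 42 and 43, independent centers, no true effect, and a reporting shift b in SD units present only as a difference between arms.

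- Standard error of a standardised difference: sqrt(1/42 + 1/43) = 0.217 SD.
- Rejection probability: P(|Z + b/SE| > 1.96).
- At b = 0.2: b/SE = 0.2/0.217 = 0.92. The upper tail is about 0.150 and the lower tail about 0.002, together about 0.152.

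| Assumed shift (SD) | Two-sided rejection, 85 centers |
|---|---|
| 0 | 5.0% |
| 0.1 | 7.5% |
| 0.2 | 15.2% |
| 0.3 | 28.2% |
| 0.5 | 63.5% |

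With the 90 planned centers in equal arms, the 0.2 SD figure is 15.8%.

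The shifts are assumed; nothing in the documents supports one over another. Counties, not centers, were randomised (Protocol 8.4), so independence is also an assumption, and the 5% starting point depends on it. The figures describe the whole differential in reporting, of which the interviewer's identity is only a part.

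**The case against.** The strongest reply is that the plan already protects the outcomes that can be observed. Aim 2(c) is defined by pests present and debris, which is close to what the IPM Checklist records, and that checklist is kept from the consultant. The same 73-item checklist is available for practices. The self-efficacy survey is already completed by the director, so the risk there is social desirability rather than interviewer scoring. Item 14 already allows for the research assistant. All of this stands, and it limits the point to self-efficacy and whatever is drawn from the interview.

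Four stronger readings are tempting but unsupported:

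- A reader might infer that practices and pest outcomes are necessarily contaminated. No section says that the interview feeds them.
- A reader might infer that a research assistant interview would avoid the bias. Research assistants are not described as masked, they attend the intervention training (item 1) and write the pre/post summary (item 15), and directors know what they were taught whoever asks.
- A reader might infer that the Overview contradicts item 5. The Overview uses the research-staff label broadly: it also covers dust collection and activity observation, in which consultants take part elsewhere in 8.9. The label may include consultants.
- A reader might infer that the bias is confined to one arm. Control directors are interviewed by their own consultant too. A larger shift in the IPM arm is likely on the reasoning above, but it is not documented.

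**Conclusion.** The point holds within limits. The same role delivers the intervention and collects the director's post-intervention interview and self-efficacy survey. Director self-efficacy is open to reporting bias likely to be larger in the IPM arm, and it has no observed counterpart. Policies, practices and pest problems share that exposure only to the extent that they are taken from the interview. The size is unknown; about 15% false positives in place of 5% is what an assumed 0.2 SD shift would give under independence and near-equal arms, and it is not an estimate for this trial. The SAP's past tense and its count of 85 centers suggest that collection may be finished, in which case the usable remedy lies in source specification and reporting.

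**What to change.** **If any director interviews remain.** Have the research assistant conduct the post-intervention interview, and preferably both waves, at the existing checklist visit. Have the director return the self-efficacy survey directly to UCSF without it passing through the consultant. This needs no new staff. It costs some research assistant time and the rapport that the consultant has built. It reduces the bias without removing it.

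**In the protocol.** Reconcile Staff Roles item 5, item 14 and the Post-Intervention Phase text on who conducts the interview. It would help to say in the Overview whether research staff includes consultants.

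**If collection is complete.** In SAP Specific Aim 2, name the source of each outcome, and use the research assistant's checklists for practices and pest problems. State who conducted each director interview. Interpret director-reported outcomes, including self-efficacy, as open to this bias. These are text and reporting changes and need no new data.
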